This pilot study will determine the tolerance and anti-tumor efficacy of irradiated haploidentical blood mononuclear cells (irradiated allogeneic cells, IAC) in patients with high-risk hematologic malignancies who have undergone autologous or allogeneic hematopoietic stem cell therapy. There will be 2 cohorts:

-Cohort 1 will be composed of patients with high-risk non-Hodgkin lymphoma or multiple myeloma; they will have undergone high dose chemotherapy with *autologous* stem cell rescue but remain at high risk for relapse.

-Cohort 2 will be composed of patients with high-risk hematologic malignancies who have undergone an HLA-matched *allogeneic* hematopoietic stem cell transplant. The IAC will be administered either prophylactically (for those identified to be at high risk at the time of transplant) or after molecular, immunophenotypic or clinical relapse (if the patient is not a candidate for standard donor lymphocyte infusion or alternate standard therapy).

- **Primary Objective**

The primary objective is to determine the toxicity associated with the administration of IAC to patients with high-risk hematologic malignancies.

- **Secondary Objective**

To secondary objective is to determine if there is evidence of disease response associated with IAC. This will be determined by standard disease staging, use of minimal residual disease markers, and/or by clinical analysis by the Hematologic Malignancies Tumor Study Group as directed by disease and disease state.

- **Tertiary Objective**

To determine if treatment with the irradiated cells induces an immune response targeting tumor associated epitopes.

Hypotheses

-An "allogeneic effect" (enhancement of an immune reaction by the presence of a concurrent allogeneic reaction) has been demonstrated in animal studies, is operative in humans and, can be used to enhance anti-tumor responses (1-6).

-Treatment with IAC, as done previously at ██████████ will induce an "allogeneic effect" that results in a clinical anti-tumor response (6,7).

- IAC induce the production of T cells that target tumor associated epitopes (7).

Primary Endpoint(s)

- Determine the toxicities associated with administration of IAC. The anticipated/projected IAC-associated toxicities of greatest concern include:
 - Short-term toxicities: constitutional/systemic adverse events including fevers, hypotension, pulmonary infiltrates;
 - Long-term toxicities: autoimmune effects, graft-versus-host disease (GVHD), graft rejection;

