In the present study we propose to extend these studies to patients with very high-risk hematologic malignancies who have undergone *autologous* or *allogeneic* hematopoietic stem cell therapy. The hematologic malignancies tumor study group at [REDACTED] has identified 2 cohorts of patients to be studied. The first cohort has very high-risk multiple myeloma or non-Hodgkins lymphoma and will have been treated with high dose chemotherapy followed by *autologous* stem cell rescue. They have been chosen for study because the risk of relapse is very high and, in the case of multiple myeloma, disease monitoring is straight-forward. The second cohort of patients has a very high-risk hematologic malignancy that has been treated with an *allogeneic* transplant from an HLA-matched donor. These patients are chosen for study because they have a projected disease free survival of <25% following allogeneic transplant. In both cases it is hoped that the infused IAC induce and/or enhance an anti-tumor response, as was seen in the earlier [REDACTED].

c) Research Design and Methods

This is an open label study designed to determine whether IAC therapy should be developed further for patients with very high-risk hematologic malignancies undergoing hematopoietic stem cell therapy. Consenting patients will have *potential* haploidentical donors (full and half siblings, genetic parents, genetic children) who might be interested in participating identified. Potential donors will be interviewed for participation and evaluated and consented by an investigator who is not the primary treatment investigator or care provider for the patient.

Patients will receive transfusions, infection prophylaxis, nutritional support, protective isolation, and all treatment-related care per standards of the Blood & Marrow Transplant Program.

The duration of the study will be 3 years. Patients and donors will be consented up to 90 days before anticipated first treatment with irradiated cells. Patients and donors will be registered within 7 days of anticipated first treatment with irradiated cells.

Treatment Plan:

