9. Disease status: Disease status will be evaluated every 8 weeks by history, physical examination, laboratory studies and bone marrow aspirate and biopsy as indicated by disease state and clinical parameters.
10. Rh- recipients of child bearing potential who are anticipated to receive a Rh+ product will receive Rhogam at standard dose.
11. Anti-coagulant treatment of any form (Heparin/ Warfarin/ Apixaban etc. will be withheld for one day prior to harvesting of cells from the donor
12. IAC products will meet preparation and release criteria as outlined below:
 - a. Donor leukapheresis volume will be 2.5-3.0 blood volumes or as determined by blood services.
 - b. The leukapheresis product will be appropriately labeled with: 2 patient-specific identifiers, the name of the product, the product unit number, the expiration date, donor Rh/ABO type, and the statement: "Caution: New Drug – Limited By Federal Law To Investigational Use Only".
 - c. If there is a major ABO incompatibility, the product will either be split so that no more than 10 ml ABO incompatible RBC be infused/day or undergo RBC depletion to \leq 10 ml of RBC.
 - d. The product will be transported to the [REDACTED] Hospital Transfusion Services where it will undergo irradiation (25 Gy)

according to standard operating procedures. A label indicating irradiation will be attached.

e. The product will then be assigned to the patient and the released product will be transported to and administered to the patient at [REDACTED] after pre-medication of the patient with acetaminophen 650 mg PO and diphenhydramine-HCl 25 mg PO.

d) Preliminary Data

See the research significance section above and references. IAC is an effective therapy for selected patients with renal cell carcinoma. Individual responses have also been seen in AML and CML (6, [name] personal observation). There is also evidence that allogeneic cells can induce a host CD8+ T cell response directed an AML-associated epitope (7).

e) Sample Size Justification/Statistical Analysis

The primary aim of this pilot study is to see if there is acceptable tolerance (no irreversible grade 3 or higher) experimental treatment-related serious adverse effects and any disease response for 10 patients in each cohort. This will ensure that there is at least an 80% chance that the true unacceptable rate is less than 30%. The study will be closed if there is >1 irreversible grade 3 or higher experimental treatment related adverse effect in either cohort.

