If there is (1) a steroid refractory GVHD or (2) graft failure in cohort 2, then the study will stop.

The secondary aim is to determine if there is evidence of disease response to IAC. If there is evidence of disease response in either arm, additional studies will be planned.

f) Study Variables

• *Independent Variables or Interventions*

IAC infusion every 8-12 weeks as tolerated and feasible.

Toxicity will be measured by occurrence of any experimental treatment-related Adverse Events (AE) up to 12 weeks of completion of therapy. The CTCAE Version 4.0 will be utilized for the description and grading of the AE. All symptoms, signs, or diseases assessed as experimental treatment-related will be captured and graded by a study investigator and an attribution will be associated to the experimental therapy (IAC).

Attribution of the AE:

- Definite – The AE is clearly related to the experimental therapy
- Probable – The AE is likely related to the experimental therapy
- Possible – The AE may be related to the study treatment
- Unlikely – The AE is doubtfully related to the study treatment
- Unrelated – The AE is clearly NOT related to the study treatment

Any experimental treatment-related irreversible grade 3 or higher AE (definite, probable or possible) will result in that patient not receiving any further treatment. If the AE corrects completely or to Grade 1 within 2 weeks, repeat treatment as directed by protocol may be utilized. If there is more than one such irreversible experimental treatment-related Grade 3 adverse event, the study will be terminated for that cohort.

Since a major concern is that the IAC might trigger an immune response that results in steroid-refractory GVHD OR graft failure (in cohort 2), specific parameters to diminish the likelihood of these events are included in the inclusion criteria (e.g. durable engraftment and high donor chimerism). Furthermore, the study will be terminated if even a single episode of these events occurs.

Overall response rate will be defined as the proportion of patients meeting the criteria for partial response (PR), very good partial response (VGPR) and complete response (CR). Disease response will be determined by Standards of Blood and Marrow Transplant Program disease-specific parameters.

- *Dependent Variables or Outcome Measures*

Toxicity and disease response will be measured. Disease response will use standard disease-specific parameters.

g) Drugs/Devices/Biologics

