- Patients undergoing haploidentical allogeneic hematopoietic stem cell transplants are not eligible; patients undergoing < 10/10 HLA allele matched allogeneic transplant are not eligible
- Pregnant women
- Children are not eligible as the transplant program is certified as an adult only transplant program.

(5) Subject Screening - DONOR

(a) Inclusion Criteria - DONOR

- Donor must be related to patient and be partially ($\geq 3/6$ antigen) HLA-matched.
- Donor must meet all RWJ Blood Services requirements for hematopoietic stem cell donation including:
 - Age ≥ 18 years old;
 - normal hemogram (WBC $4.0-10.0 \times 10^3/\text{mm}^3$; platelet count 150,000 to $440,000/\text{mm}^3$; Hemoglobin/Hematocrit; 12.5-18 g/dl, 38 to 54%)
 - not pregnant or lactating;
 - not HIV-1, HIV-2, HCV, Hepatitis B core or HTLV-I/II seropositive; HB S ag (-); meet other infectious disease screening criteria utilized by RWJ Blood Services;
 - no uncontrolled infections, other medical or psychological/social conditions, or medications that might increase the likelihood of patient or donor adverse effects or poor outcomes;
 - meet other blood bank criteria for blood product donation (as determined by RWJ Blood Center screening history and laboratory studies).
- Male and female and all ethnic groups are eligible provided they are fluent in English.

(b) Exclusion Criteria

- Non-English speaking person
- Pregnant women
- Children are not eligible as the transplant program is certified as an adult only transplant program.

(6) Recruitment Materials

N/A

(7) Lead Site Recruitment Methods

N/A

- **Subject Randomization**

N/A

- **Secondary Subjects**

N/A

- **Number of Subjects**

- (1) Total Number of Subjects**

A total of 20 subjects will complete the study. There will be 10 patients in each cohort. There will be a donor corresponding to each patient. There may be additional potential; donors screened if a donor fails the screening.

- (2) Total Number of Subjects If Multicenter Study**

N/A

- (3) Require Number of Subjects to Complete Research**

The number of subjects needed to complete the research procedures (i.e., numbers of subjects excluding screen failures.) is 40 (twenty patients and twenty donors). Each patient will participate in the study for 3 infusions and then be followed until disease progression or 3 years. Patients will be enrolled over a 3 year period of time.

- (4) Feasibility Of Recruiting**

We expect to enroll 7 subjects per year onto this study.

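### The response rate does not require measurable disease at first IAC, so a transplant-induced CR can count as response, and follow-up to progression feeds no endpoint

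*Combined protocol and SAP*

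**What the plan says.** Section b) Research Significance says Cohort 1 was chosen for its very high relapse risk, and Cohort 2 patients because "they have a projected disease free survival of <25% following allogeneic transplant". No time point is attached to that figure.

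The opening description of Cohort 2 includes use before relapse: "The IAC will be administered either prophylactically (for those identified to be at high risk at the time of transplant", with treatment after relapse as the alternative. Patients with AML in first CR are among those eligible. Under the Treatment Plan, first IAC falls within 42 days after engraftment in Cohort 1 and within 120 days in high-risk Cohort 2, so it closely follows the transplant.

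Section f) gives the outcome measures in one sentence: "Toxicity and disease response will be measured". On efficacy it says "Overall response rate will be defined as the proportion of patients meeting the criteria for partial response (PR), very good partial response (VGPR) and complete", the last category being CR, and it leaves the criteria to the transplant program's disease-specific standards. The Secondary Objective also names MRD markers and study-group clinical analysis as ways to determine response. The Secondary Endpoint is induction of tumor-reactive host T cells. Section e) says that evidence of response in either cohort will lead to additional studies.

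On follow-up, Number of Subjects (3) says "Each patient will participate in the study for 3 infusions and then be followed until disease progression or 3 years". No relapse, progression-free, disease-free or overall survival endpoint is defined.

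**The concern.** For a patient already in CR at first infusion, a PR/VGPR/CR proportion does not separate the effect of IAC from that of the transplant. The plan could count the patient as a responder or treat the patient as not evaluable, and it does not say which. As worded, the denominator is all patients and no baseline is named, so the first reading is open. The response rate, and the decision to go on to further studies, could then reflect the transplant.

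The natural outcome for these patients is time to relapse, progression or death. The plan follows patients to progression but does not say how those observations will be reported.

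**Working it through.** **1. The plan's own figure.** Inputs: "There will be 10 patients in each cohort" (Number of Subjects (1)); the closing rule "The study will be closed if there is >1 irreversible grade 3 or higher experimental treatment related adverse effect in either cohort"; and the claim "This will ensure that there is at least an 80% chance that the true unacceptable rate is less than 30" percent (both section e). With X ~ Binomial(10, 0.30), the one-sided confidence that the rate is below 30% after x events is 1 − P(X ≤ x).
- x = 0: 1 − 0.7^10 = 1 − 0.0282 = 97.2%.
- x = 1, the most the rule tolerates: 1 − (0.7^10 + 10 × 0.3 × 0.7^9) = 1 − (0.0282 + 0.1211) = 85.1%.

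The claim reproduces. It concerns toxicity only; no sample size or precision is stated for response or relapse.

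**2. Response rate with an inert product.** Let k of 10 patients be in CR at first IAC. Assume that they are still in CR when assessed, that they have no MRD that could be measured, and that nobody else responds. The plan gives no value for k, so the whole range is shown.

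| k | All patients counted | Restricted to measurable disease at first IAC |
|---|---|---|
| 0 | 0/10 = 0% | 0/10 |
| 3 | 3/10 = 30% | 0/7 |
| 5 | 5/10 = 50% | 0/5 |
| 7 | 7/10 = 70% | 0/3 |
| 10 | 10/10 = 100% | no denominator |

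Any k of 1 or more can produce apparent evidence of response. The last row is a worst case, not an expectation.

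**3. Precision of a relapse-free proportion.** Exact (Clopper-Pearson) 95% limits are the 0.025 quantile of Beta(x, n − x + 1) and the 0.975 quantile of Beta(x + 1, n − x).
- 5 of 10: 18.7% to 81.3%.
- 6 of 10: 26.2% to 87.8%.
- 3 of 5, if only five patients in a cohort were in remission (assumption): 14.7% to 94.7%.

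**4. Why no test is proposed.** Purely as an illustration, take 25% as a null value for 10 patients at one-sided 5%. The rule is then 6 or more relapse-free, with P(X ≥ 6 | 0.25) = 0.020. Power at a true rate of 50% is (210 + 120 + 45 + 10 + 1)/1024 = 386/1024 = 38%. At least 80% power at that alternative needs about 26 patients. The 25% is also unsuitable as a null: it is an upper bound, for Cohort 2 only, counted from transplant with no horizon, whereas IAC patients have already survived to engraftment.

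**5. Follow-up passages side by side.**
- Treatment Plan item 9: disease status every 8 weeks. Section h): every 3 months.
- Schedule of Events: staging appears in the 30-day column, qualified as clinically indicated, and the table ends at completion of therapy. Number of Subjects (3) follows patients to progression or 3 years.
- Section c): study duration 3 years. Number of Subjects (3): enrollment over 3 years.

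If the 7 subjects expected per year are patients (assumption), 20 patients take 20/7 = 2.9 years. With even accrual, 20 − 2 × 7 = 6 enter after year 2. If the study closes at 3 years, those 6 have less than one year of follow-up.

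**The case against.** The strongest reply is that this is an uncontrolled toxicity pilot with mixed diseases, which could not show relapse prevention under any endpoint. That stands. A reader might infer that the choice of endpoint is what stops the trial from showing prevention. The documents do not support this: the binding limits are 10 patients per cohort and no control group.

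It is also fair to say that response is not empty for patients in remission. MRD is named as a way to determine response, and the T-cell endpoint can be measured in remission. This stands in part. MRD does not appear in the response-rate definition, and immune sampling is limited to patients with an epitope that can be monitored. The program's disease-specific standards, which are not in the documents, may contain a baseline rule, but the plan does not state one.

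A reader might infer that most of both cohorts will be in remission. No share is given. Several eligibility routes select residual or active disease, some of them by status at transplant, so status at first IAC is unknown in either direction.

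Finally, a reader might take the Removing a Subject provision on worsening condition to mean that relapses will be lost. The text does not say events go unrecorded, and it sits under a heading about adults unable to consent, so its scope is unclear. Nor is every worsening a relapse.

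**Conclusion.** The point holds in limited form. Some patients will be treated in remission, the response definition lets a transplant-induced CR count, and evidence of response is the go-forward criterion, so the rule as written can mislead. The possible distortion is k/10 per cohort, with k unstated. Response remains informative for patients with measurable disease, and the primary toxicity aim is untouched.

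The planned follow-up could support a descriptive relapse/progression-free estimate. At 5 of 10 its interval spans about 63 percentage points, so it cannot show prevention and should not be tested against the disease-free survival figure. The conclusion assumes that no baseline rule in the program's own standards already closes the gap.

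**What to change.** 1. Restrict the overall response rate, and the go-forward reading of it, to patients with measurable disease at first IAC, including MRD where applicable. Report the number in remission at that point.
2. Add a descriptive secondary outcome: relapse/progression-free survival from first IAC, with relapse, progression or death as the event. Give Kaplan-Meier curves and a 1-year estimate with confidence interval (exact where follow-up is complete), by cohort and by remission status at first IAC. Make no test against the figure below 25%.
3. Keep following patients removed for worsening condition for relapse and death. Add a sensitivity analysis that counts such removals as events; the main analysis should not, because toxicity or unrelated decline could be misclassified as relapse.
4. Reconcile the follow-up passages: the two assessment intervals, the schedule table that ends at completion of therapy, and the 3-year duration set against 3-year accrual.

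**Cost.** No additional patients are needed, and items 1 to 3 are mostly wording. It would be wrong to promise no operational cost: the schedule table shows no assessments after completion of therapy, so item 4 and continued follow-up may add data collection or extend the study. The statistical price is wide intervals and small subgroups, with possibly no response denominator in a cohort treated wholly in remission.

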Registration: Once a potential donor has been identified for respective patient, both the patient / recipient and the relative/ donor will sign consent to participate in the study. Upon signing the consent, donor will undergo protocol mandated screening for eligibility. Once donor's eligibility is confirmed both patient and donors will be registered for the study by OHRS research staff.

Each participant will be given a unique identifier code. No patient will start treatment prior to registration.

All eligible patients will be treated at [REDACTED] and receive standard treatment per Blood & Marrow Transplant Program Policies.

1. Patients in cohort 1 will be treated initially with IAC within 42 days after hematopoietic engraftment (both neutrophils and platelets). Engraftment is

defined by 3 consecutive measurements with absolute neutrophil count > 500/mm³ and platelets > 20,000/mm³ without transfusion.

2. Patients in cohort 2 with *high-risk* disease will be treated initially with IAC within 120 days after hematopoietic engraftment (neutrophils and platelets). Chimerism studies must reveal engraftment of donor CD3+ cells > 80% and there must not be any evidence of > grade I *acute* GVHD or *severe* chronic GVHD, per standard CIBMTR staging.
3. Patients in cohort 2 being treated for *relapsed* disease may receive initial treatment with irradiated allogeneic cells any time after relapse documented. They may receive disease specific therapy prior to the experimental cell therapy, but they must have recovered from the disease-specific therapy prior to the experimental cell therapy.
4. All treated patients who do not have evidence of relapse or progressive disease may be treated q 8-12 weeks for up to 3 treatments with delays up to 8 weeks as clinically indicated.
5. Donor will undergo evaluation at RWJ Blood Services within 7 days of each infusion.
6. Donors meeting eligibility requirements will be harvested by leukapheresis with targeted CD3+ (0.5-3.0 x 10⁸/kg); harvesting will be done according to FACT and AABB guidelines.
7. Donor cells (0.5-3 x 10⁸ CD3+/kg) will be irradiated (25 Gy) and infused no more than 24 hours after harvesting of the cells; in case of ABO incompatibility either RBC depletion will be undertaken or the product will be split to assure infusion of \leq 10 ml ABO incompatible RBC/day.
8. Management of cytopenias, infections, and other complications will conform to standard procedures at the discretion of the physician.

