Irradiated allogeneic cells are administered under a FDA awarded IND.

h) Primary Specimen Collection

-Standard disease monitoring q 3 months

-Immunologic studies immediately prior first infusion and 30 days after each IAC infusion; if no additional infusions administered samples will be obtained also at day +60 and day +90. No samples will be repeated within 21 days of each other.

i) Interviews, Focus Groups, or Surveys

N/A

- *Administration*

N/A

- *Study Instruments*

Standard policies and procedures of the Hematologic Malignancies and Blood & Marrow Transplant Programs of Rutgers Cancer Institute of New Jersey

Timetable/Schedule of Events: Patients and donors will be consented when they meet eligibility criteria, up to 90 days prior to anticipated first treatment. Patients and donors will be registered in ONCORE within 7 days of anticipated first treatment.

Patient Procedures	Screening (within 14 days of registration- unless otherwise noted)	Pre each cycle of IAC (- 7 days)	Q 30 days (+/- 7 days) after each IAC infusion ⁶	Completion of therapy (within 8 weeks of last protocol treatment and monitoring)
Informed Consent ¹	X			
Inclusion/Exclusion	X			
Hx, PE, ECOG Performance Status	X	X	X	X
Toxicity Assessment	X	X	X	X
Hematologic and Biochemical Profile ²	X	X	X	X
Serum Pregnancy Test (if of childbearing potential)	X	X		
Disease staging BMasp/biopsy ³	X		X	
HLA and ABO/Rh Typing	X			
Infectious Disease Screening ⁴	X	X		
Ancillary studies: immune function ⁵	X	X ⁷	X	X

1. Patients will be consented within 90 days of anticipated first treatment with irradiated cells.
2. Standard CBC, chemistry profile
3. Disease staging as clinically indicated per standards of Blood & Marrow Transplant Program
4. Infection Disease Screening per RWJ transplant services within 7 days of harvesting.
5. For patients for whom there is a disease specific epitope that can be monitored during therapy four tubes of EDTA anticoagulated blood will be collected at each time point and sent to the Immune Laboratory. No need to wait for results. These patients will be identified at baseline evaluation for collection beginning prior to 1st cycle of IAC.
6. These assessments will be performed Q 30 days until the patient receives their next IAC infusion, completes protocol therapy or comes off study.
7. No need to repeat if prior sample drawn within 21 days.

Donor Procedures	Screening	Within 7 days of each donor leukapheresis	Day of Collection

[REDACTED]

10

RESERVED FOR IRB STAMP

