DO NOT MODIFY THIS SPACE

Form

Approval Date:
Expiration Date:

4/23/2021
4/22/2022

Informed Consent ¹	X		
HLA-Typing ²	X		
Donor Evaluation ³	X		
Ancillary studies: Immune function ⁶	X		
RWJ Blood Services Evaluation ⁴		X	
CBC w/diff ⁵			X

1. Donors will be consented within 90 days prior to the patient's first treatment.
2. HLA typing may be low resolution class I. May occur at any time prior to donor evaluation.
3. Donor evaluation will occur after HLA typing and will include physician evaluation to assure all donor eligibility criteria are met.
4. To be performed as per the policies of the RWJ Blood services program. Donors will provide five 7.5ml green top tubes for ancillary studies at time of initial donation.
5. Pre-collection CBC w/diff.
6. Only for selected donors whose corresponding patient has a disease related epitope that can be monitored immunologically. Four EDTA anticoagulated tubes will be collected at screening only and sent to the Immune Laboratory.

2) Project Management

a) Research Staff and Qualifications

b) Resources Available

(1) Facilities

(2) Medical Or Psychological Resources

Blood and Marrow Transplantation Program. There are no anticipated psychological effects of the experimental treatment. Any psychological or behavioral issues that arise will be addressed with available resources.

(3) Research Staff Training

c) Research Sites

3) Multi-Site Research Communication & Coordination

N/A

a) Outside Research

N/A

4) Research Data Source/s

b) Primary Data-Subjects and Specimens

▪ Subject Selection and Enrollment Considerations

(1) Recruitment Details

[REDACTED]

(2) Source of Subjects

Patients will be patients of the Blood & Marrow Transplantation practice

(3) Method to Identify Potential Subjects

Patients under a transplant physician's care will be identified by the investigators on the study.

(4) Subject Screening - PATIENT

(a) Inclusion Criteria - PATIENT

- Age 18 or over
- Patient with disease (stage) eligible per cohort:
- **COHORT 1:** Patients undergoing high dose chemotherapy with *autologous* stem cell rescue and "high-risk" disease as defined below:
 - Diffuse large cell lymphoma or peripheral T cell lymphoma (including specified WHO subtypes) not in CT-PET complete remission at time of high dose therapy

- Diffuse large cell lymphoma with “double hit” or “double expressor” features

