- Diffuse large cell lymphoma or peripheral T cell lymphoma (including WHO specified subtypes) refractory to standard induction therapy OR relapsing within 1 year of treatment OR in greater than second CR
- Mantle cell lymphoma not in CR1
- Multiple myeloma with ONE (or more) of the following high risk features:
 - Less than very good partial remission at time of high dose therapy
 - High R-ISS (Stage III – beta 2 microglobulin ≥ 5.5 plus LDH $>$ ULN and/or del17p, t(4;14), t(14;16)) at time of diagnosis
 - Cytogenetics or FISH del17p
- **COHORT 2:** Patients with high risk disease having undergone an *allogeneic* hematopoietic stem cell transplant from a 10/10 HLA matched donor with one of the following disease subtypes:
 - AML in CR1 with high risk features (ELN) at presentation
 - Diagnostic sample with either t(6;9), t(9;22), 11q23, inv 3, -5, -7, del17p, complex cytogenetics, NPMwt-flt3ITD+, OR p53 mut. Patients whose samples have mutations in RUNX1 or ASXL1 are also eligible (unless the patient has favorable cytogenetics).
 - AML in CR1 with measurable minimal residual disease (MRD) by molecular (e.g., myeloid mutation profile, PCR for NPM1, CBF, MLL) or flow cytometry
 - AML not in CR1 (including patients with morphologic CR but with incomplete recovery, CRi)
 - MDS with complex cytogenetics, 17p deletion or p53 mutation, or JAK2 or RAS mutation
 - Treatment-related MDS or AML
 - ALL not in CR1
 - ALL with MRD
 - Any hematologic malignancy relapsed or with persistent disease after *allogeneic* hematopoietic stem cell transplant.
 - Multiple myeloma
 - NHL with chemoresistant disease at time of transplant
 - Any patient undergoing *allogeneic* hematopoietic stem cell transplant and an anticipated rate of relapse $>80\%$ based upon published data and for which there is consensus amongst the Hematologic Malignancies Tumor Study Group that enrollment is appropriate
- Availability of a genetic child, genetic parent or sibling as a potential HLA haploidentical donor
- Meets standard eligibility requirements for high dose chemotherapy with autologous stem cell rescue (COHORT 1) or allogeneic hematopoietic stem cell transplant (COHORT 2) and has signed consent for those procedures

- Male and female and all ethnic groups are eligible provided they are fluent in English.

(b) Exclusion Criteria

- Non-English speaking person

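### The listed eligibility criteria and the relapse treatment rule for Cohort 2 omit the protocol's own condition that a relapsed patient must have no standard option left

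*Combined protocol and SAP*

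**What the plan says.** The opening study description has Cohort 2 patients receive IAC in one of two ways: prophylactically, or "after molecular, immunophenotypic or clinical relapse (if the patient is not a candidate for standard donor lymphocyte infusion or alternate standard therapy". The second way is conditional, and the condition appears only there in the visible text.

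Section (4)(a), Inclusion Criteria - PATIENT, gives the Cohort 2 disease list. The one line that names relapse after transplant reads "Any hematologic malignancy relapsed or with persistent disease after" an allogeneic transplant, with no condition attached. Another line, "AML not in CR1 (including patients with morphologic CR but with incomplete recovery, CRi", could also admit a relapsed patient.

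The patient exclusions in section (b) concern language, type of transplant ("Patients undergoing haploidentical allogeneic hematopoietic stem cell transplants are not eligible", and likewise those matched at fewer than 10 of 10 alleles), pregnancy and children.

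Treatment Plan item 3 says that patients in Cohort 2 treated for relapse "may receive initial treatment with irradiated allogeneic cells any time after relapse documented". It adds: "They may receive disease specific therapy prior to the experimental cell therapy". If such therapy is given, the patient must have recovered from it.

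On enrolment, the Timetable/Schedule of Events states: "Patients and donors will be consented when they meet eligibility criteria". It also schedules an inclusion/exclusion check at screening. Under (3) Method to Identify Potential Subjects, patients under a transplant physician's care "will be identified by the investigators on the study".

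**The concern.** A condition on who may receive an experimental cell product after relapse is stated in the narrative description. It is absent from the places where a screener or monitor would look for it. A relapsed patient who could still have a donor lymphocyte infusion, or another standard treatment, satisfies the disease line and meets no exclusion. That patient also meets item 3 once relapse is documented. The opening description says the same patient should not be treated.

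The stake is patient protection. The section on subject risk says that the hazards of these cells are not fully known, and the section on foreseeable risks names graft-versus-host disease and graft rejection as possible long-term effects after an allogeneic transplant. Whether standard options must be exhausted first should be settled by a criterion that can be checked at screening.

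**Working it through.** No arithmetic bears on this point, so the check compares the texts and looks for any other place that restores the condition.

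1. **Opening description, Cohort 2.** Relapse use is allowed only if no standard donor lymphocyte infusion or other standard therapy is open to the patient. Condition present.

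2. **Inclusion list, Cohort 2.** There are 11 disease lines, counting the diagnostic-sample detail as part of the first. One of the 11 names relapse after transplant. Condition absent.

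3. **Other inclusion items that might carry it indirectly.** The item on standard eligibility requirements concerns fitness for the transplant itself, not options after a later relapse. Study-group consensus is required only under the last Cohort 2 line (anticipated relapse rate above 80%) and does not reach the relapse line. Condition absent.

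4. **Patient exclusions.** There are 4, and none concerns remaining standard therapy. Condition absent.

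5. **Treatment Plan.** Item 2 sets chimerism and graft-versus-host conditions for the high-risk group, so the Treatment Plan is a place where this protocol puts treatment conditions. Item 3, the matching rule for relapse, requires documented relapse and recovery from any prior therapy. Prior therapy is permitted, not required. Condition absent.

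6. **Registration.** Research staff register patient and donor once the donor's eligibility is confirmed. No check of the patient's remaining standard options is named.

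The result for a relapsed patient with a standard option still open:

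| Text applied | Outcome |
|---|---|
| Opening description | IAC not to be given |
| Inclusion list and exclusions | Passes |
| Treatment Plan item 3 | May start once relapse is documented |

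Two details limit the comparison. The opening description names relapse but not persistent disease, so the mismatch is established only for the relapsed half of the inclusion line. And a relapsed patient may enter by a different line, such as AML or ALL not in first remission, so amending the relapse line alone would leave a route open.

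**The case against.** The strongest reply is that nothing here conflicts. The Cohort 2 list is introduced as a list of disease subtypes, while the opening description governs when the cells are given, and both can be followed at once. Item 3 comes after two items that set time windows of 42 and 120 days from engraftment. Read in that sequence, it says mainly that relapsed patients have no such window. Section f) Study Variables also refers to durable engraftment and high donor chimerism as inclusion criteria, although they appear in the Treatment Plan and not in the bullet list. The protocol itself therefore treats conditions outside the list as criteria for entry.

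Much of this stands. The opening description does still bind, and item 3 is chiefly about timing. A reader might infer that the protocol waives the condition or sanctions IAC ahead of standard therapy. The documents do not support that: silence in the list and in item 3 does not cancel a restriction stated elsewhere in the same protocol. Patient identification by study investigators within the transplant practice also makes an oversight less likely.

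What the reply does not do is put the condition where enrolment is decided. The engraftment and chimerism conditions at least appear in the Treatment Plan; this one appears in neither the Treatment Plan nor the list. Clinical judgement lowers the risk but is not a written criterion that can be verified.

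A further objection is that an undated clause could collide with item 3: a patient who may have disease-specific therapy first might be called a candidate for standard therapy and so be shut out. That is correct, and the fix has to deal with it.

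**Conclusion.** The concern holds as a failure of the operative criteria to carry a binding condition. Applied as written, the list and item 3 let through a relapsed Cohort 2 patient whom the cohort description excludes.

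The size cannot be estimated. The documents do not say how many of the 10 planned Cohort 2 patients will be relapsed, or how many of those would still have a standard option. A range from none to all 10 would carry no information. Each such patient would be 1/10 = 10% of the cohort.

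A reader might also infer an effect on graft-versus-host disease, graft failure or the stopping rules. Nothing in the documents supports one, and the planned sample size and stopping limits stay as they are.

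The conclusion assumes that the condition is not restated in text unavailable for review. The recruitment details are blacked out and the consent pages were removed, and neither was relied on. It is worth correcting because it concerns patient protection and the correction is short.

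**What to change.** Make the same addition in two places: the relapsed part of the Cohort 2 inclusion line, and Treatment Plan item 3. In item 3 it should apply to every relapsed Cohort 2 patient, whichever disease line was used for entry. Suggested sense: *and, at registration and after any disease-specific therapy given for the relapse, is unsuitable for a standard donor lymphocyte infusion and for any other standard therapy.*

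The timing matters for two reasons. It keeps prior therapy allowed under item 3, because suitability is judged after that therapy. It also places the judgement close to treatment: registration falls within 7 days of the anticipated first infusion, whereas consent may be up to 90 days before it.

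The sponsor should state whether the condition also covers persistent disease. If entry was meant to be broader, the opening description should be corrected instead, so that all three places agree.

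The cost is one clause used twice and one decision. The downside is a somewhat narrower relapsed pool, which the opening description already specifies. Recruitment slack may be small: if the expected 7 subjects per year are patients, 3 years gives 7 × 3 = 21 against the 20 needed. The protocol also counts donors as subjects elsewhere, and it does not say whether that rate allowed for the condition.
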